3. RESEARCH DESIGN/ PROTOCOL

A multi-centre, randomized, wait-list controlled trial will be used to compare the effects of tailored PA coaching sessions *versus* no coaching on PA behaviour, psychosocial factors, and health outcomes. Eligible individuals will be randomly assigned (1:1) to either the experimental (PA coaching sessions) or wait-list control condition. Groups will be stratified by injury level, age, and site. The randomization sequence will be generated by a research assistant independent of the trial. For an overview of the protocol see Figure 1.

Figure 1. Study Overview

Day 1 testing measures include vascular measures (arterial pulse wave velocity, arterial structure, and flow mediated dilation; 30 minutes), cardiac structure and function measures (30 minutes), administration of the demographics and Health Action Process Approach model questionnaire (25 minutes), and a measurement of energy expenditure at different sub-maximal wheeling speeds to calibrate MVPA cut-points (35 minutes) for a total duration of 2 hours. Participants will be given an accelerometer to wear for the 6-day monitoring period (6.1.2) after which they will return for Day 2 testing.

Day 2 testing measures include administration of the PARA-SCI (45 minutes), a peak oxygen uptake test (45 minutes), and at baseline, the first PA coaching session will be

administered (30 minutes) whereas at post-test a semi-structured interview will be administered (30 minutes). Total duration of day 2 testing will be 2 hours. The intervention protocol is described below. During the intervention, physical activity will be sampled at two time points; accelerometer and PARA SCI data will be taken during week 4 and week 7. Following the intervention, follow-up assessments of physical activity will be sampled monthly for 12 months in the intervention group only using the Leisure Time Physical Activity Questionnaire.

INTERVENTION

Intervention Protocol:

Experimental participants will receive weekly PA coaching sessions. Each session will be 10-15 minutes in duration and delivered either face to face, over Skype, or when the former modes are unavailable, over the phone. These sessions will be recorded using a portable audio recorder. Additionally, supplemental resources may be emailed to the participants based on need throughout the intervention.

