Control participants will complete baseline and post-testing only. Following completion of post-test measures they will be administered the same PA coaching session as the intervention group, with post-test measures being repeated upon intervention completion.

Standardization across sites

The intervention will take place in Vancouver for the months of April to July and in Kelowna from August to October. The same equipment brand and model will be used between sites where available. All intervention content, psychological, and fitness measures will be delivered by the same researcher. Although vascular and cardiac measures will be administered by different researchers in Vancouver and Kelowna, all technicians are experienced in their respective techniques, decreasing the likelihood of human error.

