5. OUTCOME MEASURES

All measurements will be collected at the International Collaboration on Repair Discoveries (ICORD) in the Blusson Spinal Cord Centre or the University of British Columbia Okanagan.

Primary Outcome Measure: Physical activity

6.1.1: Physical Activity Recall Assessment for People with Spinal Cord Injury (PARA-SCI):

Participants will be asked to complete a 3-day PA recall (PARA-SCI) guided by the coinvestigator ([name]). The recall assessment will take approximately 30 minutes to complete.

6.1.2: 6-day Physical Activity Monitoring Period

Participants will be fitted with a wrist-based tri-axial accelerometer to be worn 24 hours a day for 6 days in order to determine intensity and amount of PA. They will keep a detailed PA diary recording all leisure time PA performed during the day. The primary outcome will be minutes of PA per day equivalent to moderate intensity or higher (\geq 3 SCI METs determined from individual calibrations, see 2.14) from a tri-axial wrist-worn accelerometer (GT9X, ActiGraph LLC, FL). During the intervention, the accelerometer will be picked up and dropped off to the participant's home to decrease burden. Text or email reminders (i.e. "Please don't forget to wear your accelerometer today") will be used to promote adherence to accelerometer wear.

Measurement of energy expenditure during different sub-maximal wheeling speeds for calculation of moderate-vigorous physical activity during the 6-day physical activity monitoring period

We will assess energy expenditure during different sub-maximal wheeling speeds on a treadmill (self-selected slow, medium, fast) to establish cut points relating wrist-based accelerometer counts to intensity of PA in SCI. Participants will be required to push at each of the 3 speeds for 5 min/stage to ensure steady state is reached. Resting heart rate (Polar T31 heart rate monitor, Polar Electro Inc., Woodbury, NY, US), brachial artery blood pressure (CarescapeTM V100; GE Healthcare,

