Buckinghamshire, UK) will be measured two minutes prior to wheeling. Heart rate will be measured continuously throughout the test and blood pressure will be measured again at the end of each stage. Breath-by-breath gas exchange indices will be assessed using an online system (sensorMedics V Max). We will then relate activity counts from the accelerometer to energy expenditure in SCI METs (1 SCI MET = $2.7 \text{ml/kg/min})^{23}$ to determine individualized cut-points for habitual PA monitoring and the subsequent determination of the amount of moderate-to-vigorous PA (≥ 3 SCI METs). Individuals classified as ASIA D (have preserved muscle function below the level of injury) who do not use a wheelchair will not complete the treadmill cut-point evaluation for safety reasons (e.g. tripping while walking). Instead, able-bodied cut-points will be applied. In addition to the wrist accelerometer, a hip accelerometer and a pedometer will be worn to validate the wrist-based values for participants classified as ASIA D.

6.1.3: Leisure Time Physical Activity Questionnaire

Participants will be asked to complete a 7-day PA recall (LTPAQ) guided by the coinvestigator ([name]). The recall assessment will take approximately 5 minutes to complete and will be done either in-person or over the phone.

Secondary Outcome Measure: Psychosocial factors influencing PA participation

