6.2.1 Health Action Process Approach Model Measure

This survey will examine psychological factors that may affect PA participation. The survey will be recorded either electronically or with pen and paper depending on the respondent's preference. Survey will take approximately 25 minutes to complete, and will assess constructs related to exercise such as perceived risks, self- efficacy, planning, and social support. The demographics questionnaire will also be administered with this measure.

6.2.2 Semi-Structured Interview:

A semi-structured interview will be conducted at the end of the intervention to understand what components were and were not effective. Data will not be recorded. This feedback will be used to improve future iterations of the intervention.

Tertiary Outcome Measure: Arterial stiffness

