6.4.4 Aerobic Fitness Evaluation: Peak oxygen uptake test (VO2peak)

Participants will perform a graded arm ergometer test on an electronically braked arm ergometer (Angio Rehab arm ergometer, Lode, Groningen, the Netherlands), height adjusted so that the shoulder joint is aligned with the crank axis of the ergometer. Blood pressure (Dinamap Carescape V100; GE Healthcare, Buckinghamshire, UK) and respiratory measures (Quark CPET, Cosmed, Rome, Italy) will be collected two minutes prior to exercise. Heart rate will be recorded at one-second intervals via a chest strap heart rate monitor (Garmin, Schaffhausen, Switzerland). For participants with tetraplegia who have limited handgrip function, gloves (Active Hands, Solihull, Great Britain) will be used to secure hands to the ergometer handles. Participants will be instructed to maintain a cycling rate of 50 revolutions per minute (rpm) for the duration of the test. After an initial warm-up at 0W, power output will be increased each minute at a rate of 2-5 W/min for participants with tetraplegia, or 10 W/min for participants with paraplegia, until volitional exhaustion (i.e. dropping below 30 rpm). Ratings of perceived exertion (Borg 6-20 scale)²⁵ will be collected in the final 10-seconds of each stage. Oxygen consumption will be recorded on a breath-by-breath basis for the duration of the test and reported as rolling 30-second averages sampled at 5-second intervals as per consensus recommendations²⁶. This test is used to determine participants' peak oxygen uptake, ventilatory threshold and maximum heart rate.

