9. CONFIDENTIALITY

The investigator will ensure that the anonymity of each participant is maintained and identity is protected from unauthorized parties. A unique identification number will be assigned to each participant upon study entry, which will be used to identify them for the duration of the study.

Any reports or publications about the study or any other research will not include the participant's name or any other personal identification information. If the participant desires, the investigator will provide access to the published results of the study. Participant names will not be placed on any mailing lists or sold to anyone for marketing purposes. The Research Ethics Board may have access to information about participants and data regarding the performance of the treatments on a confidential basis.

All data collected (electronic or hardcopy documents) will be coded with the unique identification numbers and stored on a password-protected computer or in a locked filing cabinet in a secure laboratory space only accessible to the study investigators. This includes data from the accelerometers and audio recordings. When data is needed to be transferred, data will be transferred via password protected zipfolder to an encrypted, password-protected USB until it is downloaded onto the password-protected computer at UBCO. The online questionnaire is administered by the UBC-hosted version of FluidSurveys. All data will be stored and backed up in Canada. All data will be kept for 5 years after publication, after which it will be destroyed.

Contact information will be used to organize testing/ training sessions and for payment only unless you have indicated that you would like to be contacted for future studies. This research is part of a PhD thesis. Results will become publically available on cIRcle (http://circle.ubc.ca).

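### The coaching researcher also delivers the HAPA survey and the VO2peak test with no masking described, so these outcomes can shift in the coached arm only

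*Combined protocol and SAP*

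**What the plan says.** Section 3, Standardization across sites, states: "All intervention content, psychological, and fitness measures will be delivered by the same researcher". The arrangement is offered as a way of keeping the two sites comparable. The same paragraph gives the vascular and cardiac measures to other researchers, who differ by site. No section mentions masked outcome assessment or masked scoring.

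Sections 3 and 7 give the experimental arm nine weekly coaching sessions. Controls are not coached until after their post-test.

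On the measures themselves:

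- **HAPA constructs (6.2.1).** "The survey will be recorded either electronically or with pen and paper", as the respondent prefers. Section 9 adds: "The online questionnaire is administered by the UBC-hosted version of FluidSurveys".
- **VO2peak (6.4.4).** A graded arm-ergometer test that the participant continues to voluntary exhaustion, defined by cadence falling under 30 rpm. No rule on encouragement is given.
- **PARA-SCI (6.1.1).** Participants "complete a 3-day PA recall (PARA-SCI) guided by the coinvestigator", whose name has been removed from the public text.
- **Accelerometer (6.1.2).** Daily minutes at moderate or higher intensity from the wrist device are named as the primary outcome.

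Section 8 tests hypothesis ii by independent-samples t-tests on the post-intervention HAPA constructs. It tests hypothesis iii by regressing change in health and fitness outcomes on change in physical activity.

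**The concern.** One person delivers the intervention and then collects outcomes that respond to the participant's relationship with that person. Using a single assessor for both arms controls differences between raters. It does not control this problem, because at post-test the coaching relationship exists in one arm only.

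The overlap is closest for hypothesis ii, which belongs to the primary objective in section 2. The coach works with participants on constructs such as self-efficacy and planning, then delivers the questionnaire that asks about them. A participant who wants to show that the coaching worked can answer accordingly. The planned t-tests compare post-test scores directly, so any such shift is read as a coaching effect.

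For VO2peak the route is effort. Encouragement by someone who knows the arm can prolong the test. If coached participants also raise their activity, a lift in VO2peak confined to that arm would look like the association that hypothesis iii predicts, should both arms be pooled in the regression (section 8 does not say).

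**Working it through.** **Step 1: which outcomes the overlap reaches.**

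| Outcome | Collected by | Nature | Use in section 8 |
|---|---|---|---|
| HAPA constructs | the coaching researcher (section 3) | self-report survey | hypothesis ii, post-test t-tests |
| VO2peak | the coaching researcher (section 3) | physical test, effort-dependent | hypothesis iii, regression |
| Accelerometer minutes | device (6.1.2) | not interview-based | hypothesis i; named primary in 6.1.2, instrument not named in section 8 |
| PARA-SCI | a co-investigator (6.1.1) | guided recall | instrument not named in section 8 |
| LTPAQ | a co-investigator (6.1.3) | guided recall | none stated |
| Vascular and cardiac | other researchers (section 3) | device and imaging | hypothesis iii, regression |

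The overlap is stated for the first two rows only. Section 3 says the LTPAQ follow-up is "sampled monthly for 12 months in the intervention group only using the Leisure Time Physical Activity Questionnaire", so it supplies no between-group contrast for assessor bias to distort.

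**Step 2: what a shift would do to the hypothesis ii test.** The plan gives no figure on this point to reproduce.

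Inputs:

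- n = 15 per arm as recruited, or 12 per arm as required before the allowance for dropout (section 4).
- α = 0.05 (section 4), taken as two-sided because the plan does not say.
- The test is the independent-samples t-test of section 8.
- The shift b, in SD units, is an **assumption** with range 0.1 to 0.5, because the documents give no size.

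With no true effect and a shift b in the coached arm:

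- degrees of freedom = 2n − 2
- noncentrality = b × √(n/2)
- rejection probability = P(|T| > t at 0.975), with T noncentral t

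For n = 15, df = 28 and √(15/2) = 2.739. Noncentrality is 0.3 × 2.739 = 0.822 and 0.5 × 2.739 = 1.369.

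For n = 12, df = 22 and √(12/2) = 2.449. Noncentrality is 0.3 × 2.449 = 0.735 and 0.5 × 2.449 = 1.225.

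| Assumed shift (SD) | 15 per arm | 12 per arm |
|---|---|---|
| 0 | 5.0% | 5.0% |
| 0.1 | 5.8% | 5.6% |
| 0.2 | 8.3% | 7.6% |
| 0.3 | 12.5% | 10.8% |
| 0.5 | 26.2% | 21.6% |

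These are rates for one construct. Section 8 plans a t-test for each of several.

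**Step 3: what removing part of a shift buys.** On the same table, cutting a 0.5 SD shift to 0.3 SD with 15 per arm lowers the false-positive rate from 26.2% to 12.5%. It does not restore 5%.

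**The case against.** Several points on the other side have force.

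- **The primary outcome.** A reader might infer that the trial's primary result is collected by the coach. The documents do not support that. The variable named as primary comes from a wrist device, and the PARA-SCI is given to a co-investigator who is nowhere said to coach. Overlap is possible, since the Day 2 baseline visit combines the PARA-SCI, the VO2peak test and the first coaching session. But section 6 calls the coaching role both personal trainer and research assistant, and a removed name cannot settle the matter.
- **Interviewer bias.** The two measures known to be delivered by the coach are a survey and a physical test; neither is described as an interview. Some participants may already complete the survey online and alone. Nothing says the coach is absent or does not see the answers, so the exposure is reduced rather than excluded.
- **Prior contact.** Controls also meet this researcher, at baseline testing. The difference between arms is nine weeks of coaching, not all contact.
- **The size is assumed.** This is correct. The arithmetic shows what a shift would do, not that one exists.
- **Unmasked participants.** In a wait-list design participants know their arm, so some self-report bias remains whoever collects the data. This stands, and it limits what any fix can claim.
- **A different PARA-SCI interviewer at no cost.** A reader might suppose that the vascular or cardiac researchers could take it over. Section 3 puts their measures on Day 1 and the PARA-SCI on Day 2, and no staffing plan is given. Site-specific interviewers would also give up the consistency across sites that the plan wants.

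**Conclusion.** The concern holds for the HAPA survey and the VO2peak test. The plan says that one researcher both coaches and delivers these measures, describes no masking, and has one coached arm at the between-group post-test. Hypothesis ii is the more exposed, because its test is an unadjusted post-test comparison of self-reports.

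The possible size is illustrative: 12.5% or 26.2% false positives per construct with 15 per arm (10.8% or 21.6% with 12) if the shift is 0.3 or 0.5 SD. It rests on an assumed shift, no true effect and a two-sided test. No comparable figure is offered for VO2peak, whose planned analysis is a regression.

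The concern does not extend to the accelerometer outcome as collected. For the PARA-SCI the finding is a gap in the protocol: it does not say whether the interviewer also coaches. This matters for hypothesis i only if the PARA-SCI can stand in for the accelerometer. That is not closed off at present, because section 4 powers on weekly minutes without naming an instrument and section 8 names none.

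This does not invalidate the design. It warrants a change because the main steps are cheap.

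**What to change.** 1. **HAPA survey.** At every time point, have it self-completed on the existing online platform or on paper, with the coach absent and not shown the answers. If the coach takes the participant's stage of motivation from this survey, pass on that item alone or ask it separately.
2. **VO2peak.** Write one fixed encouragement script and use it in both arms at every test.
3. **Device data.** Process accelerometer and gas-exchange files for the analysis under coded IDs that reveal neither arm nor time point. Section 9 already assigns participant codes; a separate file code would hide the time point. Any baseline activity figure the coach needs for goal setting can be supplied outside this masked run.
4. **Hypothesis i.** State in sections 4, 5 and 8 that accelerometer minutes are the sole primary measure and that the PARA-SCI is supportive. State who leads the PARA-SCI and whether that person also coaches.
5. **Reporting.** Say that participants were unmasked and that self-report bias may remain in the HAPA results.

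**Cost.** Protocol wording and slightly more data handling. Less help will be on hand during the survey, which may matter for participants with limited hand function. Sample size, visits and the intervention are unchanged, and none of these steps requires a new outcome assessor.

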4. RECRUITMENT

A total of 30 participants with a chronic (>1 year post injury) spinal cord injury between 18-65 years of age will be recruited. Individuals must be competent to give informed consent, and be able to propel an arm ergometer.

Exclusion Criteria:

- History and/or symptoms of CVD or cardiopulmonary problems/disease.
- Major trauma or surgery within the last 6 months.
- Active Stage 3 or 4 pressure ulcer (based on the National Pressure Ulcer Advisory Panel classification)
- Recent (within 1 year) history of lower-extremity or non-union fracture
- Any unstable medical/psychiatric condition or substance abuse disorder that is likely to affect their ability to complete this study.
- Individuals with active medical issues such as pressure sores, urinary tract infections, hypertension, or heart disorders.
- Any cognitive dysfunction or language barrier that would prevent subjects from following English instructions.
- Subjects may be excluded at the discretion of the principal investigator due to other, unforeseen, safety issues.

Sample size calculation: Our study is powered to detect a significant condition X time effect for our primary outcome measure, min/wk of PA. A previous single-group study of adults with SCI tested the effects of a PA-enhancing intervention delivered by a peer and a fitness trainer (Latimer-Cheung et al., 2013). That study found very large, significant effects for change in min/wk of PA (d = .96). Given our two-group design, we are powering for a more modest interaction effect (d = .75). Twelve participants/condition (N = 24) are needed to yield a significant effect of this magnitude in a repeated measures ANOVA, with $\beta = .80$ and $\alpha = .05$. To account for study dropouts, we are budgeting for an N of 30.

Potential participants will be identified through a variety of recruitment strategies including: posters which will be distributed among hospital locations and local community venues (e.g. local sports venues, community program centres); social media advertising (i.e., website, Facebook, Twitter); email; and at the individual's request (some participants have previously provided consent to be contacted for future studies).

5. OUTCOME MEASURES

All measurements will be collected at the International Collaboration on Repair Discoveries (ICORD) in the Blusson Spinal Cord Centre or the University of British Columbia Okanagan.

Primary Outcome Measure: Physical activity

6.1.1: Physical Activity Recall Assessment for People with Spinal Cord Injury (PARA-SCI):

Participants will be asked to complete a 3-day PA recall (PARA-SCI) guided by the coinvestigator ([name]). The recall assessment will take approximately 30 minutes to complete.

6.1.2: 6-day Physical Activity Monitoring Period

Participants will be fitted with a wrist-based tri-axial accelerometer to be worn 24 hours a day for 6 days in order to determine intensity and amount of PA. They will keep a detailed PA diary recording all leisure time PA performed during the day. The primary outcome will be minutes of PA per day equivalent to moderate intensity or higher (\geq 3 SCI METs determined from individual calibrations, see 2.14) from a tri-axial wrist-worn accelerometer (GT9X, ActiGraph LLC, FL). During the intervention, the accelerometer will be picked up and dropped off to the participant's home to decrease burden. Text or email reminders (i.e. "Please don't forget to wear your accelerometer today") will be used to promote adherence to accelerometer wear.

Measurement of energy expenditure during different sub-maximal wheeling speeds for calculation of moderate-vigorous physical activity during the 6-day physical activity monitoring period

We will assess energy expenditure during different sub-maximal wheeling speeds on a treadmill (self-selected slow, medium, fast) to establish cut points relating wrist-based accelerometer counts to intensity of PA in SCI. Participants will be required to push at each of the 3 speeds for 5 min/stage to ensure steady state is reached. Resting heart rate (Polar T31 heart rate monitor, Polar Electro Inc., Woodbury, NY, US), brachial artery blood pressure (CarescapeTM V100; GE Healthcare,

Buckinghamshire, UK) will be measured two minutes prior to wheeling. Heart rate will be measured continuously throughout the test and blood pressure will be measured again at the end of each stage. Breath-by-breath gas exchange indices will be assessed using an online system (sensorMedics V Max). We will then relate activity counts from the accelerometer to energy expenditure in SCI METs (1 SCI MET = $2.7 \text{ml/kg/min})^{23}$ to determine individualized cut-points for habitual PA monitoring and the subsequent determination of the amount of moderate-to-vigorous PA (≥ 3 SCI METs). Individuals classified as ASIA D (have preserved muscle function below the level of injury) who do not use a wheelchair will not complete the treadmill cut-point evaluation for safety reasons (e.g. tripping while walking). Instead, able-bodied cut-points will be applied. In addition to the wrist accelerometer, a hip accelerometer and a pedometer will be worn to validate the wrist-based values for participants classified as ASIA D.

6.1.3: Leisure Time Physical Activity Questionnaire

Participants will be asked to complete a 7-day PA recall (LTPAQ) guided by the coinvestigator ([name]). The recall assessment will take approximately 5 minutes to complete and will be done either in-person or over the phone.

Secondary Outcome Measure: Psychosocial factors influencing PA participation

